### 1.2.3. Exploratory Endpoints

The tertiary and PD endpoints include:

- Change from Baseline in sputum mucins (total, MUC5AC, and MUC5B)
- Change from Baseline in epithelial sodium channel (ENaC) messenger ribonucleic acid (mRNA) levels from bronchial brushings
- Change from Baseline in inflammatory biomarkers from bronchoalveolar lavage (BAL)
- Change from Baseline in functional respiratory capacity (FRC) and residual volume (RV)
- Change from Baseline in regional lung volumes as measured by high resolution CT scanning (HRCT)

#### 1.2.3.1. Pharmacokinetic (PK) Endpoints

Plasma exposure over time will be summarized using data from PK profile samples collected following the first and last dose in a subset of patients, as well as trough samples collected in all patients throughout the study. In addition, potential PK/PD correlation on relevant biomarkers may be evaluated.

## 2. BACKGROUND AND RATIONALE

### 2.1. Overview of Disease

Chronic Bronchitis (CB) is an inflammatory disease of the bronchi, especially the central bronchi, and is characterized by excessive mucus secretion. Classically this is defined as significant sputum production for at least 3 months for at least 2 successive years. Abnormalities in mucus production and properties are critical to the pathophysiology of the disease. Patients suffer from varying degrees of chronic cough, sputum expectoration, and dyspnea. CB is 1 of the 2 underlying diagnoses for COPD, the other being emphysema. COPD is characterized by progressive and incompletely reversible airflow obstruction.

Chronic Bronchitis is quite common in the general population, with a wide range of 3.4%-22.0% of the adult population. This variability is caused largely by the varying definitions of CB ([Kim and Criner 2015](#)). It appears that CB affects approximately 10 million individuals in the U.S., interestingly including significant number of individuals without a diagnosis of COPD ([de Oca et al. 2012](#)). Among COPD patients those with CB have greater smoking exposure, more symptoms, and worse general health than the general COPD population. In the COPD Gene study the prevalence of CB in the COPD population was 26.2% using the classical definition and 39% using a definition based on the SGRQ ([de Oca et al. 2012](#)).

Airway mucus obstruction appears to play an important role in the pathogenesis of chronic inflammation and infection that drives the disease progression in COPD ([Fahy and Dickey 2010](#)). Multiple studies have demonstrated that CB in COPD patients is associated with accelerated lung function decline, increased risk of exacerbations, and increased mortality. As a

result of the increased exacerbation rates in CB there are greater number of emergency room visits and hospitalizations. In a large cross-sectional study of COPD patients in Belgium the number of exacerbations was 2.08 per year for the CB group vs. 1.05 in the non-CB group (Corhay et al. 2013). Some 37.3% of patients with CB had 2 or more exacerbations per year as compared to 14.2% without CB. Similar trends were seen in the COPD Gene and SPIROMICS studies. As exacerbation rates are high in CB, an emphasis on reduction of these rates has been pursued. Roflumilast is a phosphodiesterase-4 (PDE4) inhibitor which has been shown to reduce exacerbation rates only in patients with CB, but not in a general COPD population.

Bronchodilators remain the mainstay of treatment for all patients with COPD. However, no therapy has been demonstrated to reduce the mortality rate in COPD or decrease the rate of progression of the disease. There remains a significant unmet medical need for additional therapeutic interventions.

## 2.2. Therapeutic Rationale

Chronic Bronchitis is a disease of chronic mucus hypersecretion which predisposes patients to lower respiratory infections and is linked to disease progression and mortality. The study by Kesimer also found that airway mucin concentrations are linked to COPD severity (Kesimer et al. 2018) and may be a biomarker of CB. The airway in CB has been demonstrated to be dehydrated as a result of dysregulated ion transport along with an increase in goblet cells and mucus production (Graeber et al. 2013). A recent study suggested that the mucus hyperconcentration along with airway adherence is more important than the loss of mucous transport in bronchitic airway pathology (Livrighi-Butrico et al. 2017). This adherent mucus blocks airflow, which is in part responsible for reduced lung function, but more importantly is the site of bacterial airway infections. Furthermore, the mucus plugs themselves are pro-inflammatory, probably through local epithelial hypoxia which induces interleukin-1 (IL-1) and interleukin-8 (IL-8) secretion. It has been demonstrated that cigarette smoke induces ENaC activity, which results in sodium absorption from the airway and thereby hyper-concentrated airway mucus (Downs et al. 2013). It has been demonstrated that a potent and selective ENaC inhibitor with a long duration of action can indeed increase airway surface liquid (ASL) height and airway hydration (Astrand et al. 2015). In a woodsmoke murine model, an ENaC ASO resulted in a decrease in airway mucus and inflammation (Ionis data on file). Additionally, delivery of the ENaC ASO in a NEDD4L mouse model of cystic fibrosis resulted in a decrease in mucus gene expression (Gob5, Muc5ac) and a decrease in neutrophilic inflammation (Crosby et al. 2017). There was significant improvement in airway hyperreactivity. When ION-827359 was dosed in healthy volunteers there was a decrease in mucus mRNA including Gob5 and MUC5AC. Therefore, ION-827359 may be effective in treating an underlying defect in CB, specifically the increased mucus production and the hyper-concentrated mucus which result in impaired airflow and recurrent infections.

## 2.3. ION-827359

### 2.3.1. Mechanism of Action

[REDACTED]  
[REDACTED]  
[REDACTED]  
[REDACTED] Maximal antisense-mediated reduction of target mRNA levels is typically greater than 90% of control levels in sensitive tissues (Crooke and Bennett 1996; Zhang et al. 2010). Furthermore, reduction in target mRNA levels using this approach correlates directly with a subsequent reduction in target protein levels.

### 2.3.2. Chemistry

[REDACTED]  
[REDACTED]  
[REDACTED]  
[REDACTED]  
[REDACTED]  
[REDACTED]  
[REDACTED]  
[REDACTED]  
[REDACTED] The phosphorothioate modifications impart *in vivo* stability to the molecule by providing resistance to nucleases but also confer a substantial PK benefit by increasing the binding to plasma proteins, preventing renal excretion of ASOs (Geary et al. 2008). [REDACTED].

Two (2) of these segments, the 3 nucleotides at both the 5' and 3' ends, contain constrained ethyl or cEt modifications to the sugar moieties (Seth et al. 2008). [REDACTED]  
[REDACTED]  
[REDACTED]  
[REDACTED]  
[REDACTED]  
[REDACTED]  
[REDACTED]  
[REDACTED]

[REDACTED] Uniformly modified ASOs are not capable of eliciting RNase H1-induced catalytic cleavage of complementary mRNA (Monia et al. 1993). The gapmer design provides greatly improved metabolic stability and affinity to ASOs and maintains RNase H1-mediated antisense activity.

### 2.3.3. Preclinical Experience

Detailed information concerning the preclinical studies conducted with ION-827359 can be found in the Investigator's Brochure.

### 2.3.4. Clinical Experience

The safety and tolerability of ION-827359 has been evaluated in a Phase 1 clinical trial in 64 healthy volunteers. Please refer to the Investigator's Brochure for a detailed description. This study was a single-ascending dose (SAD) / multiple-ascending dose (MAD) study with 4 cohorts of 8 patients in each part. Doses in the SAD study ranged from 3 mg to 100 mg nebulized. In the MAD study the doses ranged from 10 mg to 75 mg with 5 doses over 4 weeks,

except for the final cohort where 10 doses were given. ION-827359 was well-tolerated without any serious adverse event (SAEs) or adverse events (AE) of concern. There were also no changes in clinical or laboratory measures, including no evidence of hyperkalemia. There is currently on-going a MAD trial in adult patients with cystic fibrosis.

## 2.5. Benefit-Risk Assessment

Detailed information concerning the benefit-risk assessment of ION-827359 can be found in the Investigator's Brochure. However, there are no known risks associated with ENaC inhibition in the lung. Genetic mutations leading to loss of ENaC function result in pseudohypoaldosteronism in which these patients have difficulty managing sodium balance in the body. This may result in renal sodium wasting, hyponatremia, and hyperkalemia. These were not seen in the Phase 1 study of ION-827359 but subjects will be monitored for these in this trial.

Due to the current COVID-19 pandemic, there may be risks to the patients by traveling to research sites. Sites should follow their specific regional guidance (i.e., institutional, local, state, federal, country-level, as applicable) with regard to receiving patients for clinical trials. Visits should continue as long as it is deemed safe to do so. Additional mitigation steps and a study pause may be necessary as conditions warrant. Post-treatment follow-up visits may be done remotely, if necessary. If a study patient becomes infected with COVID-19 or develop COVID-19-related symptoms, the patient should notify the study staff/Investigator and notify their treating Physician that they are participating in a clinical trial with ION-827359. To our knowledge, ION-827359 has no immunosuppressive effects.

The known potential risks to study participants associated with ION-827359 are elaborated on in the Guidance to Investigator section of the Investigator's Brochure.

### **2.5.1. Overall Assessment of Benefit:Risk**

Taking into account the measures taken to minimize risk to patients participating in this study, the potential risks identified in association with ION-827359 are justified by the anticipated benefits that may be afforded to patients with CB.

## **3. EXPERIMENTAL PLAN**

### **3.1. Study Design**

This will be a Phase 2a, double blind, randomized, placebo-controlled, dose-ranging study. Patients with CB associated with COPD will be randomized to ION-827359 or matching placebo administered by oral inhalation once weekly for 13 weeks.

### **3.2. Number of Study Centers**

This study will be conducted at multiple centers in Europe.

### **3.3. Number of Patients**

Approximately 180 patients are planned to be enrolled in this study. Patients will be randomized to ION-827359 at a dose of 37.5 mg, ION-827359 at a dose of 75 mg, or placebo.

### **3.4. Overall Study Duration and Follow-up**

The study will consist of Screening, Treatment, and Post-Treatment Periods. Please refer to the Schedule of Procedures in [Appendix A](#).

The study for an individual patient will generally consist of the following Periods:

- A  $\leq$  4-week Screening Period. The last week of which is the Run-in Period
- A 13-week Treatment Period during which study medication (ION-827359 or placebo) will be administered by nebulization once per week (both in-clinic and at home dosing)
- A 10-week Post-Treatment Period

Patients may be required to attend additional visits for monitoring of AEs or abnormal investigation results. The frequency of additional monitoring will be determined by the Study Medical Monitor in consultation with the Investigator.

#### **3.4.1. Screening**

Subject eligibility for the study will be determined within 4 weeks prior to study entry.

#### **3.4.2. Treatment**

Eligible patients will report to the Study Center for study treatment as per the Schedule of Procedures in [Appendix A](#). Study medication (ION-827359 or placebo) will be administered once per week, for 13 weeks with dosing both in-clinic and at home.

**3.4.3. Post-Treatment**

Patients are to return to the Study Center for follow-up visits on Study Days 92 and 120. The final study visit will be Study Day 162.

**3.5. End-of-Study**

The End-of-Study is defined as last patient, last visit when all patients have completed the last visit of the Post-Treatment Period.

**4. PATIENT ENROLLMENT****4.1. Screening**

Before patients may be enrolled into the study, the Sponsor or designee requires a copy of the Study Center's written Independent Ethics Committee/Institutional Review Board (IEC/IRB) approval of the protocol, informed consent form, and all other subject information and/or recruitment material.

Patients or their legally acceptable representatives must sign the consent form before any screening tests or assessments, including fasting prior to screening blood draws, are performed. At the time of consent, the subject will be considered enrolled into the study and will be assigned a unique screening number before any study procedures, including screening procedures, are performed. At the time of randomization, patients will be assigned a unique subject identification number. This number will be used to identify the subject throughout the trial and must be used on all study documentation related to that subject. The screening number and subject identification number must remain constant throughout the entire trial. In the event the subject is re-consented and re-screened the subject must be given a new screening number. Screening numbers and subject identification numbers, once assigned, will not be re-used.

**4.2. Randomization/Registration**

Patients will be randomized, after all Baseline and Screening assessments have been completed and after the Investigator has verified that they are eligible per criteria in Sections 5.1 and 5.2. No subject may begin treatment prior to randomization and assignment of a unique subject identification number.

Using an Interactive Voice/Web-Response System (IXRS), eligible patients will be randomized in a 2:2:1:1 ratio to receive ION-827359 37.5 mg (1.5 mL), ION-827359 75 mg (3 mL), Placebo 1.5 mL, and Placebo 3 mL, respectively. Cohort A will be defined as those subjects receiving 1.5 mL of Study Drug or placebo, and Cohort B as those receiving 3 mL of Study Drug or placebo. These cohorts will run concurrently.

There will be 4 separate and independent randomizations:

- PK subgroup: approximately 24 patients
- HRCT subgroup: approximately 60 patients
- Bronchoscopy subgroup: approximately 18 patients
- Other: patients who are not in the above 3 subgroups, approximately 78

The randomization lists will be prepared by an independent external vendor. Sites will be designated as to which subgroups they will be participating in. All subjects at those sites will contribute to the specific subgroup, unless the subject refuses to consent to the procedure in which case they may enroll into the Other subgroup.

#### **4.3. Replacement of Patients**

Patients who withdraw from the study will not be replaced.

#### **4.4. Unblinding of Treatment Assignment**

The Sponsor and all patients, monitors, and Study Center personnel related to the study, will be blinded throughout the study. However, if a subject has suffered a SAE (as defined in Section 9.3.3), and/or when knowledge of the treatment assignment will impact the clinical management of the subject, the Investigator will have the ability to unblind the treatment assignment for that subject using the automated interactive response technology (IRT) system. The Sponsor or designee will be informed of the unblinding of a subject within 24 hours. An unblinded randomization schema will be maintained securely at the Sponsor's designated vendor. In addition, all suspected unexpected serious adverse reaction (SUSAR) will be unblinded by the Sponsor or designee for the purpose of regulatory reporting (see Section 9.2).

Every reasonable attempt should be made to complete the early termination study procedures and observations (see [Appendix A](#) and [Appendix B](#)) prior to unblinding, as knowledge of the treatment arm could influence subject assessment.

An unblinded interim analysis may be performed and the results summarized by treatment group at the end of the Treatment Period of the study.

### **5. SUBJECT ELIGIBILITY**

To be eligible to participate in this study candidates must meet the following eligibility criteria at Screening and randomization.

#### **5.1. Inclusion Criteria**

1. Must have given written informed consent (signed and dated) and any authorizations required by local law and be able to comply with all study requirements
2. Males or females. Aged 40–70 inclusive at the time of informed consent
3. Females must be non-pregnant and non-lactating, and either surgically sterile (e.g., tubal occlusion, hysterectomy, bilateral salpingectomy, bilateral oophorectomy) or post-menopausal (defined as 12 months of spontaneous amenorrhea without an alternative medical cause and follicle stimulating hormone (FSH) levels in the post-menopausal range for the laboratory involved)

Males must be surgically sterile or abstinent\*, if engaged in sexual relations with a female of child-bearing potential, the subject must be using a condom and a highly effective contraceptive method by the partner from the time of signing the informed consent form until at least 10 weeks after the last dose of Study Drug (ION-827359 or placebo).

\* Abstinence is only acceptable as true abstinence, i.e., when this is in line with the preferred and usual lifestyle of the patient. Periodic abstinence (e.g., calendar, ovulation, symptothermal, post-ovulation methods), declaration of abstinence for the duration of a trial and withdrawal are not acceptable methods of contraception.

4. BMI  $< 35.0 \text{ kg/m}^2$
5. Patients with a diagnosis of COPD as defined by the American Thoracic Society (ATS)/European Respiratory Society (ERS)
  - Ability to perform acceptable and reproducible spirometry
  - Post-bronchodilator (4 puffs of albuterol) spirometry at Screening demonstrating the following:
    - FEV1/ forced vital capacity (FVC) ratio of  $< 0.70$
    - FEV1  $\geq 50\%$  and  $\leq 90\%$  of predicted normal
6. Clinically stable COPD in the 4 weeks prior to Screening (Visit 1)
7. Current and former smokers with smoking history of  $\geq 20$  pack years
8. Meet SGRQ definition of CB (See Section 6.1.1)
9. CAT score  $\geq 10$

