## 6. STUDY PROCEDURES

### 6.1. Study Schedule

All required study procedures are outlined in [Appendix A](#), [Appendix B](#) and [Appendix C](#).

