### 6.3. Restriction on the Lifestyle of Subjects

#### 6.3.1. Contraception Requirements

Male subjects must refrain from sperm donation and either be abstinent† or, if engaged in sexual relations with a woman of child-bearing potential (WOCBP), the subject must use a condom and the subject's non-pregnant female partner must use a highly effective contraception method from the time of signing the informed consent form until at least 10 weeks after their last dose of Study Drug. Highly effective contraception for the male subject comprises a vasectomy with negative semen analysis at Follow-up. Highly effective contraception for WOCBP partners of male subjects comprises surgical sterilization (e.g., bilateral tubal occlusion), hormonal contraception associated with inhibition of ovulation (combined estrogen and progestogen containing, or progestogen-only), intrauterine contraception device or intrauterine hormone-releasing system (IUS). Male subjects with partners that are pregnant must use condoms to ensure that the fetus is not exposed to the Study Drug.

For subjects who are exclusively in same sex relationships contraceptive requirements do not apply. If a subject who is in a same sex relationship at the time of signing the ICF becomes engaged in a heterosexual relationship, they must agree to use contraception as described and as outlined in the protocol and ICF.

**†Note:** Abstinence (i.e., refraining from heterosexual intercourse throughout the duration of study participation) is only acceptable as true abstinence, i.e., when this is in line with the preferred and usual lifestyle of the patient. Periodic abstinence (e.g., calendar, ovulation, symptothermal, post-ovulation methods), declaration of abstinence for the duration of a trial and withdrawal are not acceptable methods of contraception.

For the purposes of this study, WOCBP are defined as any female who has experienced menarche, and who does not meet 1 of the following conditions:

- Post-menopausal: 12 months of spontaneous amenorrhea in females > 55 years of age or, in females ≤ 55 years, 12 months of spontaneous amenorrhea without an alternative medical cause and FSH levels in the post-menopausal range for the laboratory involved
- 6 weeks after surgical bilateral oophorectomy with or without hysterectomy
- Posthysterectomy

**Note:** A female condom and a male condom should not be used together as friction between the 2 can result in either or both products failing.

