### **8.8. Discontinuation of Study Drug/Treatment**

A subject must permanently discontinue study treatment for any of the following:

- The subject becomes pregnant. Report the pregnancy according to instructions in Section 9.5.4
- The subject withdraws consent
- The subject experiences an AE that necessitates permanent discontinuation of Study Drug
- The subject develops laboratory test abnormalities that meet any of the stopping rules listed in Sections 8.6.1 to 8.6.3
- The subject experiences an AE that necessitates unblinding of the Investigator to the subject's treatment assignment
- Subject has PCR test positive for SARS-CoV-2

The reason for discontinuation of Study Drug must be recorded in the electronic Case Report Form (eCRF) and source documentation.

Patients who discontinue Study Drug will remain in the study and continue protocol required tests and assessments will enter the Post-Treatment Period unless consent is withdrawn. For patients withdrawn for reasons other than withdrawal of consent every effort should be made to complete the early termination of study procedures and observations at the time of withdrawal (see [Appendix A](#)) and ideally within 2 weeks from the last dose of Study Drug. If the patient declines or is unable to participate in the above, the Investigator should clarify what type of follow-up the subject is agreeable to: in person, by phone/mail, through family/friends, via correspondence/communication with other physicians, and/or from review of the medical records. Wherever possible these patients should continue to be followed up via the agreed means to collect information on AEs, concomitant medications and survival status. At the very least, the patient's status at the end of the protocol defined Study Period should be ascertained and documented wherever possible. The agreed means of follow-up will be documented in the patient records and notified to the Sponsor.

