## Appendix A. Schedule of Procedures (Continued)

Study Week/Day	Screen	Run-in Period	Treatment Period (13 Weeks)								Post-Treatment Period (10 Weeks) +		
			W1 D1	W3 D15	W5 D29	W7 D43	W9 D57	W13 D85	W14 D92 (and Early Term)	W15 D99 	W18 D120	W24 D162	
Visit Window (Days)	NA	± 1	NA	± 2	± 3	± 3	± 3	± 2	± 5	± 5	± 5	± 5	
Scheduled Visit Number	1	2	3	4	5	6	7	8	9	9a	10	11	
HRCT scans 	X								X				
Adverse Events	X	X	X	X	X	X	X	X	X	X	X	X	
Concomitant Medications	X	X	X	X	X	X	X	X	X	X	X	X	
PK Blood Sampling 			X a, e	X a	X a		X a	X a, e	X	X	X	X	

Note: If not specifically labeled, "X" means anytime. S, Screening Day, D, Day, W, Week

\* Subjects that terminate early during the Post-Treatment Period should complete all procedures for Study Day 162

+ Post-Treatment Period visits can occur remotely, if necessary.

 Full physical exam to be given at Screening and abbreviated physical exam to be given during Treatment and Follow-up Period as indicated to assess changes from Screening

 BP, heart rate (HR), respiratory rate (RR), temperature, and pulse oximetry

 Women who are not surgically sterile

 For subjects in the bronchoscopy subgroup

 Fasting only for the screening lab. During this time the patient can drink water and they should ensure that they consume sufficient water in order to not become dehydrated

 If the platelet value, serum creatinine or liver enzyme tests are uninterpretable (e.g., due to clumping, hemolysis or quantity not sufficient) or missing a repeat blood specimen should be re-drawn as soon as possible (ideally within 7 days)

 If hematuria or 2+ proteinuria is observed, see confirmation guidance in Section 8.5

 Stored at -80 °C. Can be used for follow-up exploration of laboratory findings and/or AEs (e.g., measurement of cytokine and/or chemokine levels, measurement of additional markers of kidney function, measurement of antibodies, etc.) in this or subsequent clinical studies of ION-827359

 Urine test at Screening. Day 1 can be done at the site using established methods, e.g., a breathalyzer or urine test

 Height at Visit 1 only

 If time is not specified PK draw can be done anytime

 At-home dosing to occur on Days 8, 22, 36, 50, 64, 71, and 78 (± 1 day)

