
 
• Sodium
 
• Potassium
 
• Chloride
 
• Bicarbonate
 
• Total protein
 
• Albumin
 
• Calcium
 
• Magnesium
 
• Phosphorus
 
• Glucose
 
• BUN
 
• Creatinine
 
• Cholesterol
 
• Uric Acid
 
• Total bilirubin
 
• Direct (conjugated) bilirubin
 
• Indirect (unconjugated) bilirubin
 
• ALT
 
• AST
 
• Alkaline phosphatase
 
• Creatinine kinase
 
• GGT
 
• eGFR (calculation)
 
	
 
• HBsAg
 
• Hepatitis C antibody
 
• HIV antibody
 
• FSH (women only)
 
• Serum <math>\beta</math>hCG
 
• Drug/Alcohol screen
 
 
Sputum
 
 
• Total Mucin
 
• MUC5AC
 
• MUC5B
 
 
Coagulation
 
 
• aPTT (sec)
 
• PT (sec)
 
• INR
 
	
 
• Red blood cells
 
• Hemoglobin
 
• Hematocrit
 
• MCV, MCH, MCHC
 
• Platelets
 
• White blood cells
 
• WBC Differential (%) and absolute)
 
• Neutrophils
 
• Eosinophils
 
• Basophils
 
• Lymphocytes
 
• Monocytes
 
 
Pharmacokinetics
 
 
• ION-827359 concentrations in plasma
 
	
 
• Hs-CRP
 
 
BAL Biomarkers
 
 
• Cell count and diff
 
• IL-8
 
• IL-5
 
• IP-10
 
• TGF-<math>\beta</math>
 
 
Urinalysis
 
 
• Color
 
• Appearance
 
• Specific gravity
 
• pH
 
• P/C Ratio
 
• Protein
 
• Blood
 
• Ketones
 
• Urobilinogen
 
• Glucose
 
• Bilirubin
 
• Leukocyte esterase
 
• Nitrate
 
• Microscopic examination
 

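### The only eligible women whom Section 6.3.1 still classes as of child-bearing potential, those with a tubal procedure only, are exempt from the single scheduled βhCG

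*Combined protocol and SAP*

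**What the plan says.** Five parts of the protocol bear on this point.

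- **Section 5.1, inclusion 3.** Women must be neither pregnant nor lactating. They must also be "surgically sterile (e.g., tubal occlusion, hysterectomy, bilateral salpingectomy, bilateral oophorectomy) or post-menopausal". The age range is 40 to 70. Section 5 adds that "candidates must meet the following eligibility criteria at Screening and randomization".
- **Section 6.3.1.** For this study, "WOCBP are defined as any female who has experienced menarche, and who does not meet 1 of the following conditions". The conditions are menopause, at least 6 weeks since bilateral oophorectomy, and hysterectomy. Tubal procedures are not among them. The same section names bilateral tubal occlusion as a contraceptive method for a partner of child-bearing potential.
- **Appendix A.** FSH and βhCG share one row, marked at Screening only (S-28 to S-7). Footnote 3 to that row reads "Women who are not surgically sterile".
- **Appendix B.** Serum βhCG is listed among the screening tests, with no note on who receives it.
- **Sections 8.8 and 9.5.4.** A suspected pregnancy on study leads to a test. The mandatory reasons for stopping Study Drug include "The subject becomes pregnant. Report the pregnancy according to instructions in Section 9.5.4".

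**The concern.** Being non-pregnant is a condition of entry in its own right. Inclusion 3 does not infer it from sterility. For most women, either a scheduled test or a surgical fact that Section 6.3.1 accepts as ending child-bearing potential supports that condition. Women whose only sterilisation is tubal have neither, unless they are also post-menopausal.

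What is at stake is fetal exposure to an investigational antisense drug in a woman who is dosed directly. The protocol takes even indirect exposure seriously: "Male subjects with partners that are pregnant must use condoms to ensure that the fetus is not exposed to the Study Drug". One footnote governs two hormones that serve different purposes. Exempting surgically sterile women makes sense for FSH, which establishes menopause. It fits βhCG less well when the sterilisation is of a kind that Section 6.3.1 does not accept as ending child-bearing potential.

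**Working it through.** No trial statistic enters this point. The check is to take each type of woman who might be screened and apply the three rules to her.

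Rules:

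- Child-bearing potential (6.3.1) = not post-menopausal, and not at least 6 weeks after bilateral oophorectomy, and not after hysterectomy.
- Scheduled βhCG now (Appendix A, footnote 3) = 1 if not surgically sterile as inclusion 3 uses the term, otherwise 0.
- Scheduled βhCG under the fix = 1 if not surgically sterile, or if of child-bearing potential under 6.3.1, otherwise 0.

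| Woman at Screening | Eligible under inclusion 3 | Child-bearing potential (6.3.1) | Tests now | Tests under fix |
|---|---|---|---|---|
| Tubal procedure only, not post-menopausal | yes | **yes** | **0** | **1** |
| Tubal procedure only, post-menopausal | yes | no | 0 | 0 |
| Hysterectomy | yes | no | 0 | 0 |
| Bilateral oophorectomy, 6 weeks or more ago | yes | no | 0 | 0 |
| Not sterile, post-menopausal | yes | no | 1 | 1 |
| Not sterile, menopause not established | no | yes | 1 | 1 |

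The first row is the only one that is both eligible and of child-bearing potential, and its scheduled count is 0. Two possible exceptions were checked.

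- *Could a woman be post-menopausal under inclusion 3 but not under 6.3.1?* No. Inclusion 3 requires 12 months of amenorrhea without another medical cause plus FSH in range at every age. 6.3.1 requires that only up to age 55 and less above it.
- *What about bilateral oophorectomy less than 6 weeks ago?* Inclusion 3 would accept it and 6.3.1 would not. Exclusion 1 gives major surgery within 3 months of Screening as an example of a disqualifying history, so such a woman should not be enrolled.

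Timing: the Screening column runs from S-28 to S-7, so a Screening test precedes Day 1 by 7 to 28 days.

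Other testing: Section 6.1.1 adds no pregnancy test. The test on suspicion in 9.5.4 can be used before the first dose, because the Study Glossary counts a patient as on study from consent. What remains uncovered is a pregnancy that nobody suspects.

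**The case against.** The strongest defence is that the two provisions written for female participants agree with each other. Inclusion 3 and footnote 3 use the same term for sterility, and a protocol may choose to accept tubal procedures as sterility and not test. Section 6.3.1 is mostly about male subjects and their partners, and nothing in it or elsewhere says that a participant of child-bearing potential must have a βhCG. It even accepts bilateral tubal occlusion as highly effective contraception. The investigator verifies eligibility before randomization, history and examination are part of Screening, and suspicion triggers a test.

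Much of this stands. A reader might infer that footnote 3 breaches a testing rule; it does not, because no such rule is stated. A reader might also infer that Appendices A and B conflict, since Section 6.1 refers to both for required procedures and only Appendix A carries the exemption. The documents do not support that either. Section 6.2 describes Appendix B as a list of analytes, Appendix B does not even mark βhCG as being for women, and Appendix A is the text that sets who is tested and when. Nor is pregnancy in a participant left unprovided for, given Sections 8.8 and 9.5.4. And the existing test is not misdirected: it properly covers non-sterile women whose menopausal status is still open at Screening.

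What the defence does not answer is that the definition in 6.3.1 is worded for the whole study and for any female, and that being non-pregnant is a separate criterion. For the group in the first row, no scheduled test supports it.

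**Conclusion.** The point holds as a weak safeguard at entry and is minor. For an eligible woman who is not post-menopausal and has had only tubal occlusion or bilateral salpingectomy, the schedule gives 0 pregnancy tests before first dose, although Section 6.3.1 leaves her of child-bearing potential.

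The conclusion rests on reading the 6.3.1 definition as study-wide, as its wording states, and on sites following footnote 3 as written. The risk itself cannot be sized: the documents give neither the number of such women nor a failure rate for these procedures, and none is assumed here. The residual risk is expected to be small. No endpoint, analysis or sample size changes. SAP Section 1.1 records that study treatment ended on 29 April 2021, so the practical value now lies in any later protocol that reuses this text.

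**What to change.** Split Appendix A footnote 3 by hormone:

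*FSH: women who are not surgically sterile. βhCG: women who are not surgically sterile, and any woman who is WOCBP under Section 6.3.1 (including after tubal occlusion or bilateral salpingectomy only).*

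Add a cross-reference to that footnote at serum βhCG in Appendix B, for clarity. Inclusion 3 and Section 6.3.1 stay as they are, so eligibility does not change.

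The cost is one analyte, already on the Appendix B list, added to the existing Screening draw for these women, with no extra visit. Tying the test to 6.3.1 spares women with a tubal procedure whose menopause is established. A woman aged 55 or under with a tubal procedure and no FSH result would be tested by default, which is harmless. Because the test stays at Screening, pregnancy status on Day 1 itself remains untested.
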